### **10.1.3. Additional Measures**

Additional measures include:

- Change from baseline in:
  - hemoglobin A1c levels
  - weight
  - waist/hip ratio
  - cognitive function as measured by the Montreal Cognitive Assessment (MoCA) and the Digit Symbol Substitution Test (DSST)
  - erectile function as measured by the International Index of Erectile Function Questionnaire (IIEF)
- Time to first occurrence of (after randomization):
  - composite endpoint of death from CV causes, nonfatal MI, nonfatal stroke, or hospitalization for unstable angina
  - coronary, carotid, or peripheral revascularization, individually and compositely
  - any hospitalization
- Incidence of
  - any fracture
  - development of cholelithiasis

#### **10.1.3.1. Cognitive Function**

Cognitive function will be assessed using the MoCA and the DSST.

The MoCA is a cognitive screening test designed to detect mild cognitive impairment (Nasreddine et al. 2005). It assesses different cognitive domains: attention and concentration,

executive functions, memory, language, visuoconstructional skills, conceptual thinking, calculations, and orientation. It will take approximately 10 minutes to complete the test. The total possible score is 30 points; a score of 26 or above is considered normal.

The DSST is an attention-demanding psychomotor component of the Wechsler Adult Intelligence Scale (Kuo et al. 2007). This test objectively evaluates cognitive function, exploring attention and psychomotor speed. The patient will be given a symbol-digit code in which each of the digits 1 through 9 is paired with a different symbol. Below the code, a series of symbols selected from those in the code is presented in an irregular order. The patient will be instructed to draw the symbol that matches the number and to complete as many correct symbols as possible within a 120-second test period. The DSST score will be calculated as the number of correct symbol-number matches. The number of matches attempted will also be recorded.

#### **10.1.3.2. Erectile Function**

Erectile function will be assessed in male patients using the International Index of Erectile Function (IIEF), a 15-item questionnaire. This instrument evaluates 5 domains: erectile function, orgasmic function, sexual desire, overall satisfaction, and intercourse satisfaction (Rosen et al. 2002).

#### **10.1.3.3. Revascularizations**

The independent CEC will adjudicate coronary, carotid, and peripheral revascularizations. A **coronary, carotid, or peripheral arterial revascularization** procedure will be defined as a catheter-based or open surgical procedure designed to improve myocardial, carotid, or peripheral arterial blood flow. Insertion of a guide wire through a coronary guide catheter into a coronary artery or bypass graft for the purpose of PCI is considered intention for PCI. The intention to perform percutaneous peripheral arterial intervention is denoted by the insertion of a guide wire through a guide catheter into a peripheral artery. The CEC Charter will contain the final detailed event definitions used for adjudication.

Revascularization events must be reported to the CRO as soon as (for example, within 2 business days) the site staff learns of the clinical event. Study sites should send the requested source documentation to the CEC in a timely fashion for adjudication of the event.

#### **10.1.3.4. Other Measures**

A **Hospitalization** will be defined as a hospital admission (including admission to a chest pain observation unit) or a visit to an emergency department that results in a stay >24 hours.

A **Fracture** will be defined as a clinically or radiologically apparent fracture of any bone.

**Development of cholelithiasis** will be defined as any new diagnosis of cholelithiasis after randomization, as evidenced on an imaging examination (for example, ultrasound or computerized tomography scan).

Measurement of **weight** and **waist and hip circumferences** are discussed in Section [10.2.3.2](#).

## 10.2. Safety Evaluations

Investigators are responsible for monitoring the safety of patients who have entered this study and for alerting the CRO to any event that seems unusual, even if this event may be considered an unanticipated benefit to the patient.

The investigator is responsible for the appropriate medical care of patients during the study.

The investigator remains responsible for following, through an appropriate health care option, AEs that are serious or that caused the patient to discontinue before completing the study. The patient should be followed until the event is resolved or explained. Frequency of follow-up evaluation is left to the discretion of the investigator.

### 10.2.1. Adverse Events (AEs)

Lilly has standards for reporting AEs that are to be followed regardless of applicable regulatory requirements that may be less stringent.

Lack of drug effect is not an AE in clinical trials, because the purpose of the clinical trial is to establish drug effect.

Cases of pregnancy that occur during maternal or paternal exposures to investigational product or drug delivery system should be reported. Data on fetal outcome and breast-feeding are collected for regulatory reporting and drug safety evaluation.

Study site personnel will record the occurrence and nature of each patient's preexisting conditions, including clinically significant signs and symptoms of the disease under treatment in the study.

After the informed consent form (ICF) is signed, site personnel will record any change in the condition(s) and the occurrence and nature of any AEs. All AEs related to protocol procedures are reported to the CRO.

In addition, all AEs occurring after the patient receives the first dose of investigational product must be reported to the CRO.

Investigators will be instructed to report to the CRO their assessment of the potential relatedness of each AE to protocol procedure, studied disease state, investigational product, and/or drug delivery system.

Study site personnel must alert the CRO within 1 business day of the investigator's **unblinding** a patient's treatment group assignment for any reason.

Clinically significant findings from ECGs, labs, or vital sign measurements should be reported to the CRO.

If a patient's treatment is temporarily or permanently discontinued as a result of an AE, study site personnel must clearly report to the CRO the circumstances and data leading to any such discontinuation of treatment. Patients who temporarily or permanently discontinue study drug

prior to completing the study will remain in the study to be evaluated for efficacy and safety endpoints (Section 8.3.3).

Events leading to the clinical outcome of death, nonfatal MI, hospitalization for HF or unstable angina, an urgent HF visit, nonfatal stroke, or coronary, carotid, or peripheral revascularizations will be reported as study outcomes, and will not be reported to the CRO as AEs except as noted in Section 10.2.1.1.1.

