#### 10.1.2. Secondary Efficacy Measures

Secondary efficacy measures include time (after randomization) to:

- first occurrence of the composite microvascular endpoint of diabetic retinopathy requiring laser therapy, vitrectomy, or anti-VEGF therapy; development of clinical proteinuria, a 30% decline in estimated glomerular filtration rate (eGFR), or need for chronic renal replacement therapy
- first hospitalization for unstable angina
- first occurrence of each component of the composite primary endpoint
- death
- first occurrence of heart failure (HF) requiring hospitalization or an urgent HF visit

The independent CEC will adjudicate all deaths and hospitalizations for HF or unstable angina. The CEC Charter will contain the final detailed event definitions used for adjudication; however, high-level definitions for these endpoints are provided below.

- 1) **All Cause Mortality** will be defined as deaths from CV causes, deaths from non-CV causes (for example, pulmonary, renal, etc.) and deaths not attributable to a CV or non-CV cause (that is, undetermined).
- 2) **Heart failure (HF) requiring hospitalization** will be defined as new or worsening clinical symptoms and physical signs of HF that require hospitalization for additional/increased therapy. An **urgent HF visit** will be defined as an urgent, unscheduled office/practice or emergency department visit (requires clinical signs and symptoms of HF and need for additional/increased therapy).
- 3) **Hospitalization for unstable angina** will be defined as clinical symptoms of myocardial ischemia (new or worsening) that necessitates hospitalization and one of the following: new or worsening ST or T wave changes on ECG, evidence of myocardial ischemia on imaging, angiographic evidence of a lesion in a coronary artery responsible for symptoms, need for coronary revascularization procedure (PCI or CABG) during the hospitalization; AND no evidence of an acute MI.

All potential or suspected endpoint events must be reported to the CRO as soon as (for example, within 2 business days) the site staff learns of the clinical event. Study sites should send the requested source documentation to the CEC in a timely fashion for adjudication of the event.

For the composite microvascular endpoint, the following definitions will apply:

- 1) **Diabetic retinopathy requiring laser therapy** will be defined as use of laser therapy (photocoagulation) for the treatment of diabetic retinopathy.

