#### **10.2.1.1.1. Primary, Secondary, and Additional Study Endpoints Not Considered Adverse Events or Serious Adverse Events**

The following primary and secondary efficacy events will not be required to be reported as AEs or SAEs *unless* the investigator believes the event may have been caused by the study drug, drug delivery system, or study procedure:

- death,
- nonfatal MI,
- nonfatal stroke,
- hospitalization for HF or an urgent HF visit,
- hospitalization for unstable angina, or
- coronary, carotid, or peripheral revascularizations

If one of the above endpoint events is reported but does not meet a prespecified event definition detailed in the CEC Charter, as reviewed by the independent CEC, the study site subsequently will be required to report the event as an AE or SAE to comply with regulatory reporting requirements.

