#### **10.2.4. Safety Monitoring**

The blinded Lilly clinical research physician and the blinded CRO physician will monitor safety data throughout the course of the study. The CRO physician will be responsible for safety monitoring follow-up at the site throughout the course of the study. The Lilly physician will consult, as is appropriate, with the functionally independent blinded Global Patient Safety therapeutic area physician or clinical scientist, and review trends in laboratory analyses and SAEs at periodic intervals.

Clinical endpoints adjudicated as such and SAEs will be reviewed regularly for safety and efficacy by the external IDMC. The IDMC will operate under a written charter.

Lilly Global Patient Safety and CRO will review SAEs within time frames mandated by company procedures. If a death or clinical AE is deemed serious, unexpected, and possibly related to study drug, Lilly Global Patient Safety and CRO will be unblinded to comply with regulatory reporting and safety monitoring requirements. These measures will preserve the integrity of the data collected during this study and minimize any potential for bias while providing for appropriate safety monitoring.

In the event that safety monitoring uncovers an issue that needs to be addressed by unblinding at the group level, only members of the IDMC and independent statistical analysis center (ISAC), that provides support to the IDMC, can view group unblinded data and conduct additional analyses of the safety data.

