**Study Schedule, Protocol H9X-MC-GBDJ (Concluded)**

Abbreviations: ACR = albumin/creatinine ratio; ALT = alanine aminotransferase; BP = blood pressure; CV = cardiovascular; DCCT = Diabetes Control And Complications Trial Research Group; DSST = the digit symbol substitution test; ECG = electrocardiogram; eCRF = electronic case report form; EVa = Extended follow-up Visit a; EVb = Extended follow-up Visit b; FV = final visit; HR = heart rate; IFCC = International Federation of Clinical Chemistry; IIEF = International Index of Erectile Function Questionnaire; IVRS = interactive voice response system; IWRS = interactive web response system; MoCA = Montreal Cognitive Assessment; SBP = systolic blood pressure.

- a At screening (Visit 1), HR and BP should be measured in both arms in the seated position (triplicates). Only HR and BP measurements from the arm with the higher mean SBP will be recorded; this arm should be used to measure HR and BP at all subsequent study visits. Three measurements should be taken at least 1 minute apart using the same arm. Each measurement of BP/HR is to be recorded on the eCRF.
- b The order of conducting the ECG, vital sign measurements, and blood samples for laboratory testing is determined at the investigative site.
- c Solicitation of new CV or microvascular events, hospitalizations, fractures, cholelithiasis, severe hypoglycemia episodes, allergic/hypersensitivity reactions, cancer, pancreatitis, or thyroid events will be collected and recorded for all visits after randomization.
- d A serum pregnancy test is to be performed at Visit 1 in women of childbearing potential (see Section 8.2); however if this test is unavailable a urine pregnancy test should be performed. A local (urine) pregnancy test should be performed approximately every 6 months thereafter in women of childbearing potential only, unless otherwise indicated, at the discretion of the investigator.
- e HbA1c values, reference range, and standardization method used (DCCT or IFCC) will be recorded on the eCRF. Point of care HbA1c assays will not be acceptable.
- f A morning urine sample for measuring urinary albumin and creatinine and for calculation of ACR is preferred; if not available a spot urine sample will be accepted.
- g Pharmacogenetic sample will be collected 1 time only, preferably at the randomization (Visit 3), but may be collected at any later visit.
- h After Visit 3, injection instructions will be reviewed as needed.

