4.14.1. Additional Analyses of All Cause Mortality

Deaths will be analyzed on the basis of the adjudicated cause of death which will be categorized into CV death and non-CV death. Deaths with an undetermined cause will be included in CV deaths for analysis purposes. Time-to-event analyses will be performed for all deaths as well as for each adjudicated cause of death (CV death versus non-CV death and the subcategories under CV death). Incidence rates per 100 person-years of follow-up will be calculated for each type of death for each treatment group. The NNT statistic will not be provided for these analyses. These analyses will be performed using the ITT population.

A by-patient listing of all deaths and the adjudicated outcome will be provided.

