4.17.1.2. Analysis of Other Prespecified Safety Measures

Each of the following events will be analyzed using the ITT population: acute pancreatitis, serious GI events, any cancer (excluding basal or squamous cell skin cancer) and specific categories of pancreatic cancer, MTC and C-cell hyperplasia, and thyroid carcinomas, serious hepatic events, clinically significant supraventricular arrhythmias and cardiovascular conduction disorders, serious renal events, discontinuation of study drug for any reason, and immune mediated reactions including serious allergic and hypersensitivity reactions (overall and by type: rash, urticaria, bronchospasm, angioedema, systemic anaphylaxis, erythema multiforme, Stevens Johnson syndrome, toxic epidermal necrolysis, and other). The timing of the allergic/hypersensitivity reactions (immediate reaction - occurs within minutes [<60 minutes], acute reaction - occurs from 1 up to 6 hours from study drug administration, >6 hours through 7 days from study drug administration, and >7 days from study drug administration) will also be summarized and compared between treatment groups. Acute pancreatitis will be analyzed based on adjudicated events and on events as reported by investigators. The analyses of medullary thyroid carcinoma, other thyroid carcinomas, and C-cell hyperplasia will be based on adjudicated events. The analyses of clinically significant supraventricular arrhythmias and cardiovascular conduction disorders and immune mediated reactions including serious allergic and hypersensitivity reactions will be based on SAE reports. The analysis of other cancers (excluding basal or squamous cell skin cancer) will be based on events reported by investigators.

The incidence will be summarized using number and proportion by treatment group for each of the prespecified safety events. The overall number and proportion will be reported. The overall number and proportion will be calculated as the total number of patients and proportion of patients reporting the event during the entire study treatment period. In addition, incidence rates per 100 person-years will be calculated for each of the prespecified safety events. Treatment group comparison will be assessed using a Chi-square or Fisher's exact tests.

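### Exempting deaths and the events leading to them from AE/SAE reporting conflicts with the safety-event rules in Protocol 10.2.2, so some fatal cases can go uncounted in SAE-based analyses

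*Protocol*

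**What the plan says.** Protocol 10.2.1 takes a group of outcomes out of AE reporting. The list opens with "Events leading to the clinical outcome of death, nonfatal MI, hospitalization for HF or unstable angina" and continues through urgent heart failure visits, nonfatal stroke and revascularization. These events "will be reported as study outcomes, and will not be reported to the CRO as AEs except as noted in Section 10.2.1.1.1". The wording covers what led to the death as well as the death itself. Section 10.2.1.1 marks death as an exception among its SAE criteria, and SAP 4.17.2.1 repeats the list of exempt events.

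Section 10.2.1.1.1 gives two ways back into AE/SAE reporting. One is the investigator's suspicion that study drug, delivery system or a study procedure was the cause. The other is a CEC finding: "If one of the above endpoint events is reported but does not meet a prespecified event definition detailed in the CEC Charter", the site must then report it as an AE or SAE. In Protocol 10.1.2, all-cause mortality "will be defined as deaths from CV causes, deaths from non-CV causes", and undetermined deaths are added.

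On the analysis side, SAP 4.17.1.2 says that arrhythmia/conduction disorders and "immune mediated reactions including serious allergic and hypersensitivity reactions will be based on SAE reports". SAP 4.14.1 analyses all deaths and splits them by adjudicated cause ("CV death versus non-CV death and the subcategories under CV death"), with a by-patient listing of every death. Protocol 10.2.4 says: "Clinical endpoints adjudicated as such and SAEs will be reviewed regularly for safety and efficacy by the external IDMC".

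**The concern.** Exempting endpoints from expedited AE reporting is normal in an outcome trial. The difficulty is that death from any cause is one of the exempt endpoints and that the exemption extends to the events that led to it. Read literally, a site whose patient dies of a prespecified safety event that the investigator considers unrelated may file a death outcome and no AE or SAE. Some safety measures are counted from SAE reports, so the most severe cases could be absent from their own analysis. If the drug made such an event more often fatal, that measure could understate the harm.

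**Working it through.** No figure in the plan is at issue, so there is none to reproduce. The check sets the rules side by side and then illustrates what a loss of cases would do.

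**1. Can an exempt death come back into AE/SAE reporting?** Through causality, yes, but this depends on one blinded case-level judgement. Through the CEC rule, no: the three parts of the all-cause mortality definition (CV, non-CV, undetermined) leave no death outside it. This follows from the protocol's high-level definitions; the final ones are in the CEC Charter.

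**2. Which rules pull the other way?** The same section 10.2.1 requires all AEs after the first dose to be reported, and 10.2.2 has event-specific rules. Attachment 1, footnote c, adds solicitation at visits; its list ends with "allergic/hypersensitivity reactions, cancer, pancreatitis, or thyroid events will be collected and recorded for all visits after randomization" and also names severe hypoglycemia, hospitalizations, and CV and microvascular events in general. No sentence says whether these rules or the exemption prevail.

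**3. Where would a lost report matter?**

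| Measure | Capture rule in 10.2.2 | Source in SAP 4.17 | Exposure |
|---|---|---|---|
| Arrhythmia/conduction | Recorded as AE or SAE; SAE if clinically significant (10.2.2.7) | SAE reports | Yes |
| Immune-mediated | AE or SAE (10.2.2.5); allergic reactions also solicited | SAE reports | Yes |
| Serious GI, hepatic | Prospective collection (10.2.2.2, 10.2.2.6); not named in footnote c | None named | Lesser, uncertain |
| Renal | Worded as adverse events (10.2.2.8); not named as such in footnote c | None named | Lesser, uncertain |
| Pancreatitis | Adjudication triggered by AEs (10.2.2.1); solicited | Adjudicated and investigator-reported | Better protected |
| Cancer, thyroid | Prospective collection; solicited | Investigator reports; thyroid adjudicated | Better protected |
| Severe hypoglycemia | Always an SAE (10.2.2.4); solicited | Episodes by visit, source not named | Better protected |

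The general SAE and TEAE comparisons (SAP 4.17.2) depend on AE/SAE reporting throughout. SAP 4.3.3 keeps all randomized patients in yes/no event analyses, so a patient with an unreported fatal event counts as event-free.

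**4. Does the death analysis recover the case?** Only in part. Cause is subdivided within CV death alone. A hepatic or gastrointestinal death is compared between arms only as non-CV death, and otherwise appears as a line in a listing.

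**5. What would the loss do?** Inputs: 9600 patients at 1:1, so 4800 per arm (Protocol 7.3, 9.3), and two-sided 0.05. Event rates and the lost share f are assumptions. Here f is the share of cases that are fatal, judged unrelated, and not captured by any other route.

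*Equal f in both arms.* Each rate is multiplied by (1 − f), so the risk ratio is unchanged. Power = Φ(|p1 − p2|/SE − 1.96), with SE = √{[p1(1 − p1) + p2(1 − p2)]/4800}. For 1.0% versus 0.5% and f = 30%: p1 = 0.0070, p2 = 0.0035, SE = 0.001475, and 0.0035/0.001475 − 1.96 = 0.41, giving 66%.

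| True rates | f = 0 | 10% | 30% | 50% |
|---|---|---|---|---|
| 1.0% vs 0.5% | 81% | 77% | 66% | 52% |
| 2.0% vs 1.0% | 98% | 97% | 92% | 81% |

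*Unequal f.* Observed RR = true RR × (1 − f_drug)/(1 − f_placebo). For a true RR of 2.0:

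- 20% versus 10% lost: 2.0 × 0.80/0.90 = 1.78
- 30% versus 10% lost: 2.0 × 0.70/0.90 = 1.56
- 50% versus 10% lost: 2.0 × 0.50/0.90 = 1.11

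**The case against.** The best reply is that the exemption was not meant to reach these events. Acute liver failure, gastrointestinal perforation, complete heart block and anaphylaxis all fall under a collection or recording rule in 10.2.2, and none of those rules excludes fatal cases. A patient who is hospitalized or at immediate risk of dying meets an SAE criterion before death, the site has 24 hours from awareness to notify, and nothing withdraws an SAE already filed. All-cause and non-CV deaths are compared by arm.

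All of that stands, and it confines the exposure mainly to sudden or rapidly fatal events judged unrelated. It does not close the gap. No sentence gives 10.2.2 precedence over 10.2.1, and the rules in 10.2.2.5 and 10.2.2.7 work through the same AE/SAE reporting that 10.2.1 switches off.

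Three stronger readings are tempting, and the documents do not support them:

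- **A reader might infer that fatal cases of the named risks as a group drop out of the safety analyses.** Cancer, thyroid events, pancreatitis and severe hypoglycemia have routes of their own, and the hepatic and gastrointestinal rules call for prospective collection.
- **A reader might infer that the data monitoring committee (IDMC) would miss the signal.** Protocol 12.2.12 gives it information relevant to participants' safety, the synopsis has it monitor unblinded data regularly, and its charter was not available. That it sees a death only after adjudication would be an inference from one sentence.
- **A reader might put a number on the lost cases.** Assume mortality of 1.5 to 2.5% per year over 9600 × 6.5 = 62,400 person-years, giving 936 to 1560 deaths. If half are non-CV (468 to 780) and 5 to 10% of those are relevant, the result is about 23 to 78. The mortality rate and both shares are assumed. The result also supposes that every such death was judged unrelated, had no earlier SAE and escaped prospective collection, so it is a ceiling on assumed rates and not an estimate.

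**Conclusion.** The conflict is real and should be corrected. As written, fatal cases judged unrelated can be missing from the SAE and TEAE tables and from the arrhythmia/conduction and immune-mediated analyses. Hepatic, gastrointestinal and renal events are exposed to a lesser and less certain degree. Whether cases are in fact lost depends on how sites resolve the contradiction.

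The size cannot be derived from the documents. The power and risk-ratio figures above show direction and sensitivity under assumed inputs only. Equal loss in both arms costs power and leaves the risk ratio alone; bias needs a fatal share or a causality judgement that differs by arm. That the CEC rule has no trigger for a death rests on the protocol's definitions and should be checked against the CEC Charter. The primary endpoint analysis is not affected.

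**What to change.** 1. **Protocol 10.2.1 and 10.2.1.1.1:** reconcile with 10.2.2 by stating that the exemption does not stop a prespecified safety event with a fatal outcome from being recorded and counted as that event. Do not turn every 10.2.2 item into an SAE: the list includes discontinuation of study drug, and the renal criteria include macroalbuminuria found on laboratory testing.
2. **SAP 4.17.1.2:** count a patient once as having the event if it appears in AE/SAE reports, in the prospectively collected reports, or as the adjudicated cause of death.
3. **SAP 4.14.1:** tabulate non-CV deaths by adjudicated cause and arm, and supply the table to the IDMC.
4. **Deaths already reported:** reconcile them once against the adjudication material. All deaths go to the CEC, so source documents should exist.

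The cost is a short protocol clarification, two SAP changes, some additional forms and a one-time reconciliation. No visits or procedures are added.
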